- Stroke survivors > 3 months from most recent unilateral, stroke based on clinically or experimentally obtained MRI brain scans and behavioral evidence of stroke (e.g., risk factors, hemiplegia, unilateral sensory impairment, or localized higher cortical dysfunction) by report or in the medical record.
- Age: ≥21 years of age.
- Complete NIH Stroke Scale.
- Assessments performed at screening include the following:
 - Sufficient endurance, motor ability and balance to ambulate at least 10

Version 10 Revised 11/21/2014

meters continuously with moderate or less assistance.

- Demonstrate a gait impairment during ambulation such as gait instability or inefficient gait pattern
- Pass the Transcranial Magnetic Stimulation Adult Safety Screen (TASS) except for items related specifically to stroke and the treatment for stroke, i.e., neurologic injury, having a seizure related to stroke, or having a craniotomy for treatment related to stroke such as to relieve intracranial pressure.

Exclusion Criteria

- History of potentially fatal cardiac arrhythmias, such as ventricular tachycardia, supraventricular tachycardia, and rapid ventricular response atrial fibrillation with hemodynamic instability.
- Demand pacemakers or any other implanted electronic systems.
- Pregnant women, uncontrolled seizure disorder, Parkinson's Disease, Spinal cord injury, Traumatic brain injury with evidence of motor weakness, Multiple sclerosis.
- Documented episode in the medical record of a seizure occurring 1 month or more post stroke for which the patient received consultation or treatment for said seizure. Seizures occurring within the first month following a stroke are not exclusionary unless followed by another seizure.
- Fixed ankle plantar flexor contracture, peroneal nerve injury at the fibular head as the cause of foot-drop.
- History of dementia, severely impaired cognition, communication or comprehension deficits.
- Presence of severe or frequent headaches
- History of Botulinum toxin (Botox) injection to either of the lower extremities within the 3 month period preceding study entry.
- Have other medical conditions or are taking medications that compromise ambulation or balance.
- Failure to meet established screening criteria for TMS or tDCS (i.e., TASS - except as noted under inclusion criteria)
- Principal Investigator's or Medical Monitor's discretion not to include a participant

Additional Exclusion Criteria for MRI Scan

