 - A study physician trained in rescue procedures, will be on call when a subject is receiving single pulse TMS in this study. The study physician will be called by study personnel in the event of muscle contractions persisting after TMS (possible seizure) or complaints of dizziness, nausea, shortness or loss of breath, or loss of consciousness (possible syncope). Study personnel will note body parts that might be affected (e.g., the left arm or leg after right hemisphere stimulation) and/or other symptoms that might occur and report them to the study physician. [Should these be observed, the session will be terminated, and the subject will not be tested again].
 - If a subject were to have a seizure or syncopal episode during or immediately following TMS, the following precautions will be performed by study personnel:
 - The stimulator will be stopped and the coil will be removed from the subject's head.
 - The subject will be supported to physically guard against injury.
 - The subject will be placed on his/her side on a flat surface away from sharp edges.
 - The study physician will be called.
 - Emergency services will be called by study personnel to transport the subject to the emergency room if so directed by the study

- physician.
- Emergency services will be called if the study physician cannot be reached.
 - Either the study physician or the PI or subinvestigators will accompany the subject to the ER and explain the recommended post-event assessment which is as follows:
 - It is recommended that after the seizure is over, the subject will be examined thoroughly for injuries and a complete neurological exam will be completed. Routine studies, including calcium, magnesium, and prolactin, will be completed and urine will be sent for a drug screen. An MRI scan of the head will be performed to rule out underlying epileptogenic pathology. An EEG will be performed with hyperventilation and anterior temporal leads. The subject will be advised that following a seizure provoked by TMS, the likelihood of further spontaneous seizures is not significantly increased unless other pathology is discovered. The subject will be scheduled for a neurology consultation. The subject will not be allowed to drive himself/herself home. Transportation would be arranged for the subject.

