 - The PIs and study physician would provide documentation that the seizure happened during a TMS session, that it does not constitute epilepsy, and that seizures caused by TMS have not resulted in future seizures. Seizures induced during electroconvulsive therapy (ECT) for depression, for example, do not cause driving privileges to be revoked in the state of Arkansas. Like ECT, a seizure occurring after TMS would not cause driving privileges to be revoked.

Potential risks concerning MRI scan: One potential safety concern is participant internal metal during MRI scanning, which can be painful and dangerous. Screening procedures administered prior to the scan will be used to rule out any participants who may potentially be at risk for harm as a result of internal metal objects. Another potential risk involved with imaging procedure is claustrophobia. Participants are able to quit the scan at any time by indicating to the technician that they wish to do so.

Other risks:

Potential risks associated with TMS must be considered in light of the duration and frequency of stimulation⁴¹. Most of the risks which are listed below have been associated with repetitive TMS subjects in this study ARE NOT RECEIVING REPETITIVE TMS. Rather, subjects in this study are receiving single pulses of TMS. Single pulses delivered in the fashion described above involve significantly less risk and discomfort than repetitive TMS (rTMS) where 100s to 1000s of pulses are delivered in succession. Adverse events rarely associated with single pulse TMS would include the following: 1) Vasodepressor (neurocardiogenic) syncope is a common reaction to

Version 10 Revised 11/21/2014

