anxiety and psycho-physical discomfort. Syncope may occur more often than seizure during TMS testing and treatment and suspected seizure associated with TMS might actually be syncopal episodes rather than seizure²⁷ 2) Animals have shown permanent increases of the auditory threshold after high intensity single-pulse TMS⁴² and humans have shown transient increases. Subjects wear earplugs to protect hearing during TMS. 3) Human subjects have rarely experienced seizure following single pulses of TMS²⁷. In two cases, they were not healthy, normal subjects. In one case, the seizure may have been associated with brain lesions due to multiple sclerosis and with the use of olanzapine. In the second case, seizure was associated with the use of chlorpromazine and lithium and a family history of epilepsy. As mentioned above, a seizure or syncopal episode occurred during single pulse TMS in one normal subject who did not have identifiable risk factors for seizure or syncope⁴³. A study physician experienced in TMS will be on call in case of an adverse event. A thorough plan is in place to contact emergency services if necessary and to follow up if a subject went to emergency services. Subjects are fully informed of risks during the informed consent process.

Risk factors that pertain to TMS studies (but have greater relevance to rTMS than single pulse TMS) are listed below. These risk factors are assessed via the TMS adult safety screen and the exclusion/inclusion criteria for this study.

- **Likely:** Subjects may feel anxious about participation. Subjects may experience minor discomfort associated with scalp muscle twitching.
- **Less likely:** Head pain related to stimulation of underlying muscle and nerves occurs in approximately 10% of subjects. The incidence and severity is a function of stimulus site and intensity. The symptoms are typically limited to the time of stimulation and can be treated with minor over-the-counter analgesics if necessary.
- **Rare:** The following have rarely been identified with TMS:
 - Syncope (as described above).
 - Seizure induction represents the most serious known risk of rTMS⁴¹. Seizures have been reported more frequently in subjects with brain lesions (e.g., stroke) but have rarely been reported in subjects with no history of seizures or neurologic disease.

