2. All subjects will wear ear plugs during testing sessions. TMS will be stopped if an ear plug falls out during a session.
3. A study physician trained in rescue procedures, will be on call when a subject is receiving single pulse TMS in this study. The study physician will be called by study personnel in the event of muscle contractions persisting after TMS (possible seizure) or complaints of dizziness, nausea, shortness or loss of breath, or loss of consciousness (possible syncope). Study personnel will note body parts that might be affected (e.g., the left arm or leg after right hemisphere stimulation) and/or other symptoms that might occur and report them to the

Version 10 Revised 11/21/2014

study physician. [Should these be observed, the session will be terminated, and the subject will not be tested again].

4. If a subject were to have a seizure or syncopal episode during or immediately following TMS, the following precautions will be performed by study personnel:
 - a. The stimulator will be stopped and the coil will be removed from the subject's head.
 - b. The subject will be supported to physically guard against injury.
 - c. The subject will be placed on his/her side on a flat surface away from sharp edges.
 - d. The study physician will be called.
 - e. Emergency services will be called by study personnel to transport the subject to the emergency room if so directed by the study physician.
 - f. Emergency services will be called if the study physician cannot be reached.
 - g. Either the study physician or the PI or subinvestigators will accompany the subject to the ER and explain the recommended post-event assessment which is as follows:

It is recommended that after the seizure is over, the subject will be examined thoroughly for injuries and a complete neurological exam will be completed. Routine studies, including calcium, magnesium, and prolactin, will be completed and urine will be sent for a drug screen. An MRI scan of the head will be performed to rule out underlying epileptogenic pathology. An EEG will be performed with hyperventilation and anterior temporal leads. The subject will be advised that following a seizure provoked by TMS, the likelihood of further spontaneous seizures is not significantly increased unless other pathology is discovered. The subject will be scheduled for a neurology consultation. The subject will not be allowed to drive himself/herself home. Transportation would be arranged for the subject.

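### The promised statement that a seizure at a TMS session is not epilepsy carries no condition, although the same plan recommends a work-up that bears on it

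*Combined protocol and SAP*

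**What the plan says.** The plan for a seizure or syncopal episode during or just after TMS is set out in the risk-minimisation steps under Device Risks. It is repeated almost word for word under Protection Against Risks. A physician or investigator goes with the subject to the emergency room to "explain the recommended post-event assessment which is as follows". The recommended assessment includes:

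- a head MRI, with its purpose stated: "An MRI scan of the head will be performed to rule out underlying epileptogenic pathology"
- an EEG
- a neurology referral: "The subject will be scheduled for a neurology consultation"

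The subject is to be advised that, after a seizure provoked by TMS, "the likelihood of further spontaneous seizures is not significantly increased unless other pathology is discovered".

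The plan then turns to what study staff will put on record: "The PIs and study physician would provide documentation that the seizure happened during a TMS session, that it does not constitute epilepsy". A third item follows in the same sentence, that TMS-induced seizures have not been followed by later ones. The paragraph ends by reasoning from ECT for depression that a seizure after TMS would not lead to loss of driving privileges.

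Other risks, in its list of rare events, says that a seizure might affect driving, employment and insurance, and that subjects are told this at consent.

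**The concern.** Whether a seizure counts as epilepsy is a clinical judgement, and the recommended MRI, EEG and neurology consultation all bear on it. A commitment to document one answer, with no allowance for the results, does not fit a plan that seeks those results. The plan shows awareness of this in the recurrence advice, which it limits to the case where nothing else is found. The written statement lacks the same limit.

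The population makes the limit relevant. If staff followed the text as it stands, a participant with a known brain lesion, and possibly an earlier seizure, could be the subject of a signed statement that the work-up does not support. Staff would also have two different wordings on driving to work from. Participant information is at stake here; the trial's inference is not.

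**Working it through.** The plan states no figure on this point, so the check is a side-by-side reading.

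**Step 1. The three items to be documented (same in both copies).**

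| Item | Kind of statement | Condition attached |
|---|---|---|
| The seizure happened during a TMS session | Fact of the event | None needed |
| It is not epilepsy | Clinical conclusion | None |
| Past TMS seizures were not followed by others | General remark on experience | Not challenged here |

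One of the three items is a clinical conclusion, and it has no condition.

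**Step 2. What the same plan says around it.** Three recommended steps bear on that conclusion: MRI, EEG and neurology consultation. The recurrence advice carries one condition: "the likelihood of further spontaneous seizures is not significantly increased unless other pathology is discovered". So the plan qualifies what is said to the subject and does not qualify what is put in writing.

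**Step 3. Timing.** The documentation sentence comes after the work-up in the text, but nothing says whether it is written before or after the results. Even if it is written afterwards, its content is stated in advance and does not depend on them.

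**Step 4. Population.** The Inclusion Criteria require a previous unilateral stroke in everyone. They waive three stroke-related items of the TMS safety screen: neurologic injury, "having a seizure related to stroke, or having a craniotomy for treatment related to stroke such as to relieve intracranial pressure". One of the three concerns a seizure. The Exclusion Criteria add: "Seizures occurring within the first month following a stroke are not exclusionary unless followed by another seizure". A participant with one early post-stroke seizure can therefore enter. A bullet under Other risks that opens with rTMS also notes that seizures are reported more often when there is a brain lesion such as stroke.

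**Step 5. Driving.** Device Risks and Protection Against Risks say without qualification that privileges would not be revoked. Other risks says a seizure might influence them. Device Risks also promises, for the TMS used in this study, full information on the foreseeable financial and medical consequences of a seizure. The two driving wordings should therefore agree.

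**Step 6. Frequency.** The documents give no seizure rate for single-pulse TMS after stroke and no count of participants with an earlier seizure. No expected number of affected participants can be derived.

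**The case against.** The best defence is grammatical. In the documentation sentence the word *it* refers to the seizure, and the plan treats that seizure as provoked by TMS. On this reading the statement says only that a provoked event is not in itself epilepsy, and the separate question of the participant's own seizure risk is the one the plan already conditions. This is a fair reading, so the sentence need not be taken as a diagnosis of the participant. It does not remove the problem. Whether the event was provoked, or arose from the stroke lesion, is part of what the work-up would help to settle.

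A second defence is order. The documentation comes last, after the tests and the referral, and the study physician, who shares in issuing it, is nowhere told to disregard adverse findings. A reader might infer that the protocol has the statement issued before the results are in; the documents do not say so. What remains is that the content is not made to depend on the results.

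Third, the harm is limited, and this stands. The statement replaces no care, the session ends, the subject is not tested again and may not drive home. Uncontrolled seizure disorder is excluded, as are documented later post-stroke seizures that led to consultation or treatment.

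On driving, a reader might infer that the protocol contradicts itself or misstates state law. Neither is supported. To influence a privilege is broader than to revoke it, the cautious bullet opens with rTMS while this trial uses single pulses, and by the protocol's account the cautious wording is the one subjects receive at consent. The rTMS distinction helps only in part. The second copy of the flat assurance sits under a heading that names repetitive TMS, although its steps refer to single-pulse TMS in this study. The legal position cannot be checked from the documents.

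**Conclusion.** The point holds as a minor participant-safety wording issue. It consists of one unconditional clinical conclusion, written in two places, beside a work-up that bears on it and a condition the plan already uses for the recurrence advice. It has no effect on endpoints, sample size, error rates or analysis.

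The conclusion rests on taking the sentence literally and on the stated eligibility rules. It does not require that any participant has an earlier seizure or that the statement is issued early.

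The driving text is a secondary mismatch in wording. No error in the consent form is claimed, because that form is not among the material reviewed.

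**What to change.** In both copies of the seizure plan, split the documentation sentence:

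1. Record at once that the event occurred during a TMS session, and keep the general remark on past TMS experience.
2. Issue the statement that the event is not epilepsy only after the recommended work-up, and only if the neurology consultation agrees. That opinion should take account of the EEG, any MRI finding beyond the known stroke lesion, and any earlier post-stroke seizure.

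The test should be the neurology opinion and not a clear MRI. Every participant has had a stroke, so a rule that the MRI alone must support the statement could rarely be met.

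As a consistency edit, qualify the driving sentence in both places so that it matches the wording under Other risks.

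The change adds no procedure, since the MRI, EEG and consultation are already recommended. Its cost is less immediate reassurance and a later supporting statement, which matters to a participant facing the driving, employment or insurance questions that the protocol names. Issuing the factual record at once reduces that cost.

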- A weak electrical current is applied to the brain via the scalp during tDCS using two surface electrodes. Current evidence shows that tDCS applied to motor and non-motor areas according to the present tDCS safety guidelines produces only minor adverse effects in healthy humans and patients with varying neurological disorders. One published safety study of tDCS, using stimulation parameters similar to this study, evaluated 103 subjects²⁵, and found no adverse effects on cognitive and psychomotor measures, nor EEG changes during or after 20 min of treatment. In a double-blind, sham-controlled study³⁹ it has been shown that comparing tDCS and sham stimulation of the motor cortex elicited minimal discomfort and difference in the duration of tingling sensations. Another study summarized adverse effects of 567 tDCS sessions over motor and non-motor cortical areas (occipital, temporal, parietal) in 102 subjects who participated in tDCS studies⁴⁰.
 - **active** tDCS intervention causes a sensation of mild tingling and itching under the electrodes that lasts for 10 to 30 seconds. Less frequently, a burning sensation or a burn is reported. Headache, visual sensations, difficulty concentrating, nervousness or overexcitability during procedure, unpleasant sensations, dizziness, fatigue, insomnia, and nausea are infrequently reported after tDCS. Because 10-20 conductive paste is

added to the electrodes to deliver tDCS, subjects will get paste in their hair.

- Risk will be minimized by the following steps:
 - First subjects are fully informed of all risks during the informed consent process.
 - For tDCS we use stimulation parameters that are well below the maximum levels that are considered safe. We will ensure there is no skin breakdown or lesions in the vicinity of electrode placement. The electrodes have connectors on their back to eliminate the possibility of contact with scalp which could cause a burn. We monitor electrode impedances during stimulation to ensure good conductance of current to scalp.
 - For TMS, we use stimulation procedures that fall within the guidelines recommended at the conclusion of the NIH Panel on TMS (see Wasserman ⁴¹). Patients will be fully informed of the possibility of seizure, the plan for care in event of a seizure, and any foreseeable financial or medical consequences resulting from a seizure.
 - All subjects will wear ear plugs during testing sessions. TMS will be stopped if an ear plug falls out during a session.

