The PIs and study physician would provide documentation that the seizure happened during a TMS session, that it does not constitute epilepsy, and that seizures caused by TMS have not resulted in future seizures. Seizures induced during electroconvulsive therapy (ECT) for depression, for example, do not cause driving privileges to be revoked in the state of Arkansas. Like ECT, a seizure occurring after TMS would not cause driving privileges to be revoked.

Benefits

Potential benefits to subjects participating in the study include the following:

- The potential benefits to participants include personal satisfaction knowing

Version 10 Revised 11/21/2014

they have helped further research that could benefit patients with stroke and education about research studies.

- Further stroke patients could benefit from the treatment intervention in terms of increase ambulation and social well-being.
- Participants are not guaranteed a benefit from this study.

Data Safety and Monitoring

Data safety and monitoring will be performed in two ways. First, independent study monitoring will be performed by the Research Support Center at UAMS after the first 1-2 participants are enrolled. Thereafter, independent study monitoring will be performed by the Research Support Center at UAMS. Monitoring would occur according to the RSC monitoring plan. The Data and Safety Monitoring Plan describes operating procedures that will be in place to monitor compliance, study data validity and integrity, participant safety, individuals and/or entities (e.g., IRB) that will be involved in monitoring these procedures, and the frequency/regularity of this monitoring.

Adverse Events

Eliciting and Reporting Adverse Events:

Subjects will be monitored for the occurrence of adverse events throughout the study procedures.

Adverse Events Reporting and Evaluation:

All adverse events occurring during the course of the clinical study, whether device-related or otherwise, will be recorded on the Adverse Event CRF. For all adverse events, the study physician will provide an assessment of the adverse event, its treatment and resolution, and its relationship to the investigational device. All adverse events will be reported to the Sponsor and/or IRB in accordance with applicable institutional and federal regulatory guidelines.

Identification of Adverse Events:

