An adverse event is defined as any new medical problem, or exacerbation of an existing problem, experienced by a subject while enrolled in the study, whether or not it is considered device-related.

Relationship of Adverse Events to the Study Device:

The study physician will assess the relationship of the adverse event to the investigational device. The relationship will be assessed using the following categories:

- Definitely Related: A direct cause and effect relationship between the investigational device and the adverse event exists.

- Possibly Related: A direct cause and effect relationship between the investigational device and the adverse event has not been clearly demonstrated, but is likely or very likely.
- Unlikely Related: A direct cause and effect relationship between the investigational device and the adverse event is improbable, but not impossible.
- Unrelated: The adverse event is definitely not associated with the investigational device.

Unanticipated Adverse Device Effects:

An unanticipated adverse device effect is defined as “any serious adverse effect on health or safety, or any life-threatening problem, or death caused by, or associated with, a device; if that effect, problem, or death was not previously identified in nature, severity, or degree of incidence in the investigational plan, or application (including supplementary application), or any other unanticipated serious problem associated with a device that relates to the rights, safety, or welfare of subjects.”

In the event unanticipated adverse effect occurs, the investigator will report the event(s) according to federal and institutional policies.

Serious Adverse Events:

Each adverse event will be assessed for its seriousness using the criteria outlined below. The term serious adverse event is not synonymous with a “severe” adverse event, which may be used to describe the intensity of an event experienced by the subject. An adverse event will be classified as serious if it meets any of the following criteria:

- Results in, or contributes to, a death
- Life-threatening (i.e., the subject was, in the opinion of the investigator, at risk of death at the time of the event, but it does not include an event that, had it occurred in a more severe form, might have caused death)
- Results in permanent disability or incapacity (i.e., permanent impairment of a body function or permanent damage to a body structure)
- Requires in-subject hospitalization or prolongs hospitalization

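### The causality label Possibly Related is defined as a probable relationship, so an event with the device as a reasonable but not likely cause fits no definition

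*Combined protocol and SAP*

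**What the plan says.** Under Relationship of Adverse Events to the Study Device, the protocol introduces a closed list: "The relationship will be assessed using the following categories". Four levels follow.

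- Definitely Related: a direct causal link exists.
- Possibly Related: a direct causal link between the device and "the adverse event has not been clearly demonstrated, but is likely or very likely".
- Unlikely Related: a direct causal link between "the investigational device and the adverse event is improbable, but not impossible".
- Unrelated: no association at all.

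Adverse Events Reporting and Evaluation makes the grade compulsory for every event: "the study physician will provide an assessment of the adverse event, its treatment and resolution, and its relationship to the investigational device". The same section has all events, "whether device-related or otherwise, will be recorded on the Adverse Event CRF", and has all of them reported to the sponsor and/or IRB under the applicable guidelines.

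**The concern.** A causality scale works only if label and definition agree and the levels leave no gap between them. Here the second level carries a label that means *could be* and a definition that means *probably is*. The third level begins at improbable. The middle of the range, where the device is a credible candidate but not the likely cause, is left undefined.

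Two things are at stake. The first is the grade itself: the same event can be entered at either of two levels, depending on whether the grader follows the label or the definitions. The second is how the grade is read. Someone who sees only the label in a safety summary will understand something weaker than the definition says. The study runs under an IDE (Study Locations), and this is the only relatedness scale that the protocol gives the physician.

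**Working it through.** No arithmetic applies to the main point. The check is to set the definitions side by side, grade one event both ways, look for a rule that settles it, and trace where the grade is used.

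**1. Coverage of the scale**

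| Strength of the causal link | Level by definition | Level by label |
|---|---|---|
| Certain | Definitely Related | Definitely Related |
| Likely or very likely | Possibly Related | none (there is no Probably level) |
| Reasonable, but not likely | none | Possibly Related |
| Improbable | Unlikely Related | Unlikely Related |
| Excluded | Unrelated | Unrelated |

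Three of the four levels agree across the two columns. Possibly Related does not: its label and its definition sit on different rows.

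**2. One event, graded twice.** Take an event for which the device is a reasonable but not likely cause. By the label it is Possibly Related. By the definitions Possibly Related is ruled out, because the link is not likely. The only level left short of ruling the device out is Unlikely Related, and that fits only if improbable is stretched to mean anything short of likely. Neither grade satisfies both its label and its definition.

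**3. A rule elsewhere.** The sections on severity, seriousness, unanticipated device effects and anticipated events contain no tie-break. The Data and Safety Monitoring Plan and the monitoring plan of the Research Support Center are mentioned under Data Safety and Monitoring but are not among the documents, so they could not be checked.

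**4. Where the grade is used.** Recording and reporting cover all events. The definition of an unanticipated adverse device effect asks whether a serious effect was caused by or associated with a device, and does not refer to the four levels. Data Analysis covers the aims, the power calculation and the exploratory regressions, and none of them uses the grade.

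**5. Whether such events are foreseeable.** Device Risks names nine infrequent tDCS complaints: headache, visual sensations, difficulty concentrating, nervousness or overexcitability, unpleasant sensations, and then "dizziness, fatigue, insomnia, and nausea are infrequently reported after tDCS" (1 + 1 + 1 + 1 + 1 + 4 = 9). Three of the nine also appear in the TMS safety text. For headache, Other risks says: "Head pain related to stimulation of underlying muscle and nerves occurs in approximately 10% of subjects". Dizziness and nausea are among the signs that prompt a call to the physician: "complaints of dizziness, nausea, shortness or loss of breath, or loss of consciousness (possible syncope". The count shows that symptom names are shared. It does not show how often a real event would fall in the undefined band.

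**The case against.** The strongest reply is that this is an editorial slip with no demonstrated effect on grading. Several parts of it stand.

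- **Direction.** A reader might infer that such events will be graded too low. The text does not support that. A reasonable cause is not an improbable one, so Unlikely Related fits such an event by neither label nor definition, while Possibly Related at least fits by label. Downgrading is possible, not built in.
- **Disagreement between graders.** The protocol assigns the grade to the study physician and does not say how many people will grade. A single grader could apply one reading throughout.
- **Lost events.** A reader might infer that device-related events will go unreported. They will not, because recording and reporting do not depend on the grade.
- **Frequency.** A reader might infer that mixed causes are common because tDCS and TMS share symptoms. Support for this is thin. Having both at one visit rests on a single sentence in the preliminary-studies section about testing MEPs after anodal tDCS at baseline. Baseline Procedures mentions no tDCS, the Study Schedule places tDCS only in weeks 1 to 4, and TMS after baseline is planned for weeks 5 and 8. Other risks says its listed TMS risks matter more for repetitive than for single-pulse stimulation, and that head pain is usually confined to the time of stimulation. Treadmill exertion as a rival cause of dizziness or fatigue during the tDCS sessions is an inference, not a statement in the protocol.

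None of this removes the mismatch. Even a single consistent grader has to choose between the label and the definition, and a later reader cannot tell which was followed.

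**Conclusion.** Wrong as written, and minor. One of four labels contradicts its own definition, and the scale has no defined level between likely and improbable. An event in that gap can be graded Possibly by label or Unlikely by definition, and Possibly Related in a summary can be read as weaker than defined.

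On the supplied documents the impact stays within the device-relationship record. Efficacy, sample size, event capture and reporting are untouched. The documents give no rate for events in the gap, so no number of misgraded events is claimed. Confidence is high for the wording mismatch and lower for how often it would matter. The conclusion assumes that the two monitoring plans not supplied neither clarify the scale nor use the grade in a decision. If they clarify it, the point weakens; if they act on the grade, it gains weight.

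**What to change.** Keep the present second-level definition word for word and relabel it **Probably Related**. Add a level beneath it:

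*Possibly Related: a causal relationship with the investigational device is a reasonable possibility, neither likely nor improbable, including when other causes are also plausible.*

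Leave Definitely Related, Unlikely Related and Unrelated unchanged. The new definition should not require a rival cause that is at least as plausible as the device, because that would open another gap. As an illustration with assumed figures, a device judged 40% likely against two rivals at 30% each is the leading candidate, yet it is neither likely nor improbable and would again have no level.

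Re-rate any events already graded in the two middle levels; the documents do not say whether there are any. The cost is one added CRF category and a small amount of re-rating. Possibly Related will then include some events caused by something other than tDCS, so it should not be read as a count of tDCS effects.
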